## 7.4 Investigator responsibilities relating to safety reporting

All Adverse Events whether serious or not will be recorded in the hospital notes in the first instance. A record will also be kept in the participant’s CRF and the Sponsor’s AE Log. In the event of a mildly deranged blood test or clinical observation of no clinical significance to the patient (for example a mildly elevated liver function test or a mildly elevated blood pressure reading in a participant with known hypertension taking prescribed antihypertensive medication), the local PI will be informed and will sign and date the participants CRF. However it will not be necessary to complete an AE CRF or the Sponsor’s AE Log for these minor events.

SAEs or serious adverse reactions (SAR)s must be notified to the sponsor as soon as the investigator becomes aware of the event (within 24 hours). Refer to SOP and ensure the completed SAE report form is sent to the sponsor via E-mail.

The sponsor will notify all SUSARs to the NPRA electronically and the relevant ethics committee.

The sponsor will inform the NPRA and relevant ethics committee of SUSARs as soon as possible, but no later than 7 calendar days after first knowledge by the sponsor that a case qualifies. Any additional information will be reported within 8 additional calendar days. This report must include an assessment of the importance and implication of the findings, including relevant previous experience with the same or similar medicinal products. Follow-up information should be actively sought and follow-up reports should be submitted to the NPCB when it becomes available.

Serious, unexpected ADRs that are not fatal or life-threatening must be notified to the NPCB as soon as possible but no later than 15 calendar days after first knowledge by the sponsor that the case meets the minimum criteria for expedited reporting. Follow-up information should be actively sought and follow-up reports should be submitted to the NPCB when it becomes available.

**Causality Assessment** — All cases judged by either the reporting health care professional or the sponsor as having a reasonable suspected causal relationship to the medicinal product qualify as ADRs.

**Definitely** — there is clear evidence to suggest a causal relationship, and other possible contributing factors can be ruled out.

**Probably** — there is evidence to suggest a causal relationship and the influence of other factors is unlikely.

**Possibly** — there is some evidence to suggest a causal relationship (e.g. the event occurred within a reasonable time after administration of the trial medication). However, the influence of other factors may have contributed to the event (i.e. the patient's clinical condition, other concomitant events).

**Unlikely** — there is little evidence to suggest there is a causal relationship (e.g. the event did not occur within a reasonable time after administration of the trial medication). There is another reasonable explanation for the event (e.g. the participant's clinical condition, or other concomitant treatments).

**Unrelated** — there is no evidence of any causal relationship.

**Not Assessable** — Note if this description is used the sponsor will assume the event is related to the IMP until follow up information is received from the investigator to confirm a definitive causality assessment.

Any SUSAR assessed as related to the IMP will need to be reported to the Sponsor irrespective of how long after IMP administration the reaction has occurred.

Expectedness should be based solely on the available Reference Safety Information (RSI) for the

IMP and will be described using following categories :

**Expected** — an AE that is classed in nature as serious and which is consistent with the information about the IMP listed in the RSI or clearly defined in this protocol.

**Unexpected** — an AE that is classed in nature as serious and which is not consistent with the information about the IMP listed in the RSI.

The completed AE Log will be sent to Sponsor upon request and/or every 2 months.

The Chief Investigator (CI) will respond to any SAE queries raised by the Sponsor as soon as possible. Follow up reports must continually be completed within acceptable time-frames and sent to the sponsor as detailed above until the reportable event is considered resolved.

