## 7. Pharmacovigilance

### 7.1 Safety/Toxicity

All adverse events will be recorded; the investigator will assess whether those events are drug related (reasonable possibility, no reasonable possibility) and this assessment will be recorded in the database for all adverse events. This study will use the Common Terminology Criteria for Adverse Events (CTCAE V5.0) for adverse event reporting.

The AE monitoring period will commence on Day 1 of the study (start of IMP) till Day 90 of the study. Adverse events will be assessed by the worst grade and per CTCAE term from first dose until 30 days after last dose of study treatment.

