### 7.2 Reference Safety Information

A NeoART-CIN Reference Safety Information document based upon the Summary Product Characteristics for artesunate (WHOPAR., 2017) forms the Reference Safety Information for this study. Section 4.8 of the Summary Product Characteristics for artesunate (WHOPAR., 2017) lists the following potential side effects. The adverse events are listed by body system, organ class and absolute frequency. They are generally not based on adequately sized randomized controlled trials but on published literature data generated mostly during post-approval use. When frequency estimates are available they are defined as follows: very common ( $\geq 1/10$ ), common ( $\geq 1/100, < 1/10$ ), uncommon ( $\geq 1/1000, < 1/100$ ), rare ( $\geq 1/10,000, < 1/1000$ ), very rare ( $< 1/10,000$ ).

Very Common	Common	Uncommon	Rare
Blood and lymphatic disorders			
		Neutropenia Low reticulocyte count	
Cardiac disorders			
		Bradycardia	
Gastrointestinal disorders			
		Mild GI disturbances	
Hepato-biliary disorders			
		Elevated liver enzymes	
General disorders			
			Hypersensitivity (allergic reactions)

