**SERIOUS ADVERSE EVENTS SHOULD BE IMMEDIATELY REPORTED ACCORDING TO THE PROCEDURE DETAILED IN THIS PROTOCOL.**

Adverse Event (AE) — Any untoward medical occurrence in a patient or clinical investigation subject administered a pharmaceutical product and which does not necessarily have to have a causal relationship with this treatment.

An adverse event (AE) can therefore be any unfavourable and unintended sign (e.g. an abnormal laboratory finding), symptom or disease temporally associated with the use of a medicinal product, whether or not considered related to the medicinal product.

Pre-existing conditions should only be reported as an adverse event if the condition worsens by at least 1 CTCAE grade. As the IMP has a short half-life, we would expect drug clearance within 24 hours of stopping the IMP.

As part of pharmacovigilance, adverse event data will be collected from the day 1 of IMP dose until 30 days following the end of the IMP treatment schedule.

Adverse Reaction (AR) — All noxious and unintended responses to a medicinal product related to any dose should be considered adverse drug reactions.

Serious Adverse Event (SAE) or Serious Adverse Reaction (SAR) — *any untoward medical occurrence that at any dose:*

- Results in death,
- Is life-threatening,
- Requires inpatient hospitalisation or prolongation of existing hospitalisation,
- Results in persistent or significant disability/incapacity or
- Is a congenital anomaly/birth defect.

Medical and scientific judgement should be exercised in deciding whether expedited reporting is appropriate in other situations, such as important medical events that may not be immediately life-threatening or result in death or hospitalisation but may jeopardise the patient or may require intervention to prevent one of the other outcomes listed in the definition above. These should also usually be considered “serious”.

Suspected Unexpected Serious Adverse Reaction (SUSAR) — an Adverse Reaction which is classed in nature as both serious and unexpected

An ‘Unexpected Adverse Reaction’ is when both the nature and severity of the event is not consistent with the reference safety information available for the IMP in question.

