## 9. Data Collection Tool

All data will be handled in accordance with the Data Protection Act. The Case Report Forms (CRFs) will not bear the participant's name or other directly identifiable data. The participant's trial Identification Number (ID) only will be used for identification. The Sponsor Subject ID log can be used to cross reference participant's identifiable information.

Case Report Forms will be designed by the CI and the CI delegate and the final version will be approved by the Sponsor.

It is the Investigator's responsibility to ensure the The Staff Delegation of Responsibilities Log is completed and all data entered and recorded in the CRFs are accurate. The Staff Delegation of Responsibilities Log will identify all trial personnel responsible for data collection, entry, handling and managing the trial Redcap database. Basic demographic and clinical information will be gathered at the time of the initial interview and by review of the medical notes if needed.

All laboratory analysis should be reviewed by the PI and where results reported are not within the normal range the PI must clearly annotate 'Not clinically Significant' or 'Clinically significant' and sign and date the results. The relevant results should be carefully transcribed to the Case Report Forms.

In order to ensure completeness of data collected, participants will be contacted by the research team (telephone call/letter) in the event of missing data such as patient quality of life questionnaires.

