#### **10.2.3.1 Safety analyses**

Tables on AEs will report

- all AEs irrespective of their relationship to treatment
- the AEs related to the treatment (excluding those declared not reasonably possibly related to the treatment, but including those with relationship not assessable).

The worst grade of the AEs per patient and per CTCAE term over each period will be tabulated by treatment arm. The percentage of patients on each treatment arm presenting severe treatment-related AE (grade  $\geq 3$ ), of patients reported to have died of toxicity and that of patients who stopped treatment due to toxicity will also be calculated and the 95% confidence interval will be presented.

For the reporting of SAEs:

- the study safety overview table will list the number of reported SAE terms, SAR terms and SUSAR terms per treatment arm and the number of reported death and toxic death cases;
- line listings of SAEs and of SARs will be provided;
- the number of SAEs and SARs per System Organ Class and Preferred Term will be tabulated

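### Section 7.4 exempts mild laboratory findings from the AE form and log, while 7.1 and 10.2.3.1 promise to record and tabulate all AEs, so low-grade laboratory toxicity may be undercounted

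*Protocol*

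**What the plan says.** Protocol 7.1 sets the general rule, "All adverse events will be recorded", and requires the investigator's view on drug-relatedness to be entered in the database for each event. The AE definition under 7.3 says an AE can be "any unfavourable and unintended sign (e.g. an abnormal laboratory finding", and sets no threshold of clinical significance.

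Section 7.4 begins in the same spirit: every AE, serious or not, goes into the hospital notes, the participant's CRF and the Sponsor's AE Log. It then makes an exception: "In the event of a mildly deranged blood test or clinical observation of no clinical significance to the patient". The laboratory illustration is "for example a mildly elevated liver function test". In such cases the local PI is told and signs and dates the participant's CRF, but "it will not be necessary to complete an AE CRF" or the AE Log. The section itself refers to these cases as minor events.

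Protocol 10.2.3.1 says the tables will report "all AEs irrespective of their relationship to treatment", by worst grade per patient and CTCAE term. The side-effect table in 7.2 includes "Elevated liver enzymes", neutropenia and low reticulocyte count. On laboratory data, section 9 has the PI mark each out-of-range result as clinically significant or not, and adds: "The relevant results should be carefully transcribed to the Case Report Forms".

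**The concern.** The general rule, the exemption and the promised tables do not fit together. A new mild rise in liver enzymes can meet the AE definition in 7.3 and be due for recording with causality under 7.1. It would be expected in the tables of 10.2.3.1, yet under 7.4 it may never reach an AE record. The exemption turns on two judgements, that the change is mild and that it does not matter clinically. Neither is tied to a CTCAE grade, so sites may draw the line in different places. By contrast, 7.3 gives an objective rule for pre-existing conditions (worsening by at least one CTCAE grade).

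The exempted category includes a listed reaction of the drug. Section 5.1.8 says that 14 days of dosing for three cycles is longer than usual malaria treatment and calls for close pharmacovigilance. Low-grade laboratory change is part of what a small phase II study can pass on to the next trial. An exempted finding also has no stated place for the causality assessment that 7.1 requires, and it is absent from the AE Log that goes to the sponsor on request and/or every two months.

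**Working it through.** The protocol states no figure on this point, so there is none to reproduce. The check is a comparison of texts, followed by a bound on what can be said about size.

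**1. Can the sections be followed together?** Take a mild, new liver-test rise that the PI considers clinically unimportant.

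- 7.3: it can be an AE, since an abnormal laboratory finding is the example given.
- 7.1: if an AE, it is recorded and its relatedness is entered in the database.
- 7.4, opening sentences: it goes in the CRF and the AE Log.
- 7.4, exemption: no AE CRF and no AE Log entry.
- 10.2.3.1: all AEs are tabulated by worst grade, with no exclusion for exempted findings.

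The exemption contradicts the opening of its own section. It also leaves 10.2.3.1 promising a completeness that the AE records need not have.

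**2. Which way can the error go?** An exempted finding cannot enter a table built from records it was never put into, and nothing in 7.4 adds events. Any bias in the low-grade rows is therefore downward.

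**3. Number of opportunities.** Sections 6.1 to 6.4 schedule FBC, U&E and LFT at D1, D14, D22, D43, D64 and D90. D1 precedes the first dose, so five panels per patient can show toxicity on study drug. With the maximum of 28 patients (Protocol Summary), 5 x 28 = 140 panels.

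**4. Effect of one omission.** 1/28 = 3.6 percentage points for the CTCAE term concerned.

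**5. Illustration under assumptions.** Neither the true proportion p of patients with a low-grade laboratory change nor the share s of them exempted is in the protocol; both are assumed. Expected patients shown in the AE table = 28 x p x (1 - s):

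| Assumed p | Expected true count | s = 25% | s = 50% | s = 100% |
|---|---|---|---|---|
| 10% | 2.8 | 2.1 | 1.4 | 0 |
| 20% | 5.6 | 4.2 | 2.8 | 0 |
| 40% | 11.2 | 8.4 | 5.6 | 0 |

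**6. Lower end, using the protocol's own frequency band.** As extracted, 7.2 places neutropenia and raised liver enzymes in the uncommon column (at least 1/1000, under 1/100). For 28 patients that gives 28 x 0.001 = 0.03 to 28 x 0.01 = 0.28 expected cases. The chance of at least one is 1 - 0.999^28 = 2.8% to 1 - 0.99^28 = 24.5%. Section 7.2 says these frequencies come mostly from published post-approval data, and 5.1.8 says exposure here is longer. The band may therefore not carry over, but the protocol gives no other figure.

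**7. What is outside the exemption.** A finding must be both mild and clinically unimportant to be exempt. Grade 3 or higher events, SAEs, toxic deaths and stops for toxicity do not fit that description. Tolerability is measured by completion of the dosing regimen, not from AE forms.

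**The case against.** The best defence is that 7.4 is the specific rule and 7.1 the general one. The definition in 7.3 says an AE can be an abnormal laboratory finding, not that every out-of-range value is one. On that reading, trivial values are simply not AEs and nothing conflicts. This carries some weight, but 7.4 itself calls the exempted cases events, and neither 7.1 nor 10.2.3.1 mentions an exclusion.

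A second defence is that laboratory tabulations belong in a statistical analysis plan, which is not at hand. That stands as far as it goes: the lack of a laboratory table in the protocol is not the fault here. But an analysis plan can grade only values that were captured. Section 9 asks for transcription of relevant results without defining the word. It may mean every protocol-required panel, or only selected results; under the second reading a later plan could not recover the rest.

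A reader might infer that these findings vanish, or that undercounting is certain. The documents do not support either. The PI signs the participant's CRF, and out-of-range results are reviewed and annotated, so a trail remains. Section 10.2.3.1 names no data source, so the link from the tables to the AE form and log is an inference from 7.4. Whether any event is lost depends on PI judgement. Liver tests are named explicitly; blood counts come in only through the general reference to blood tests. It would also be wrong to count all six scheduled panels (6 x 28 = 168) as opportunities, because the Day 1 panel is taken before dosing.

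Finally, the named safety endpoint is SAEs at Day 90, and a single-arm trial has no between-arm comparison to distort. Both points are true, and they keep the matter small.

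**Conclusion.** The inconsistency between 7.1, 7.4 and 10.2.3.1 is real and lies in the current text. Its consequence is conditional. If the AE tables draw on the AE form and log, and if investigators use the exemption, then the low-grade laboratory rows may be too low and cannot be too high. Exempted findings would also have no stated place for the causality assessment that 7.1 requires.

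The size cannot be derived from the protocol. The firm statements are 3.6 percentage points per omitted patient per term and up to 140 scheduled post-dose panels; the table of assumed rates shows a range and predicts nothing. Summaries of grade 3 or higher events, SAEs, toxic deaths, stops for toxicity and tolerability should not change. This is a minor point, worth correcting because the remedy is cheap and one affected term is a listed reaction.

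**What to change.** Reconcile the sections; no clinical rule needs to be touched.

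- **7.1 and 7.4:** keep the exemption from the AE form, but define it by an objective recording criterion in place of the unqualified word mildly, and refer to it in 7.1 so that the general rule and its exception agree.
- **9:** state that all scheduled FBC, U&E and LFT values are entered in the CRF, whether or not the PI considers them clinically significant.
- **10.2.3.1:** state that laboratory toxicity is tabulated from those values, as worst CTCAE grade per patient and shift from Day 1, and that the AE tables exclude laboratory findings exempted under 7.4.

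The cost is some extra data entry (at most 28 x 6 = 168 panels including Day 1, of blood tests already scheduled) and some programming. Sites complete no additional AE forms on account of the exempted findings. Reported low-grade laboratory rates may look higher than they would from AE forms alone, and the report should explain why.

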#### Notification of deaths

All deaths will be reported to the Sponsor irrespective of whether the death is related to disease progression, the IMP or an unrelated event.

### 7.5 Development Safety Update Reports (DSURs)

The CI or the CI delegate will prepare the DSUR, using the Sponsor's template and in accordance with the Sponsor's SOP. It will be reviewed by the Sponsor and when necessary be referred to an independent committee (*i.e.* Research Governance Safety Sub Committee). The CI or the CI delegate will provide to the relevant ethics committee and the Sponsor will provide to NPCB the prepared DSUR annually within the defined reporting timelines.

### 7.6 Annual Progress Reports (APRs)

The CI or the CI delegate will prepare the APR in accordance with SOP. Following review by the Sponsor, the CI or the CI delegate will send to the relevant ethics committee the reviewed report. The APR is due for submission annually within 30 days of the anniversary date on which the favourable opinion was given by the ethics committee, until the trial is declared ended

### 7.7 Pregnancy

Artesunate is teratogenic in animal models and is contraindicated in the first trimester of pregnancy in humans. Pregnant women with malaria nevertheless are exposed to artesunate when no alternatives are available for treatment and studies published to date do not indicate an increased risk of teratogenicity. Pregnant women will not be recruited and participants will be required to use effective methods of medical contraception during the study. Women of child bearing age will be required to undergo a pregnancy test within 72 hours prior to commencing the study and must consent to adequate contraceptive methods from the time of consent and for up to 6 weeks following the end of IMP treatment.

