### **5.1.5 Dose and schedule modifications**

No dosage modifications will be undertaken. Any Grade 3/4 reaction (according to Common Terminology Criteria for Adverse Events (CTCAE) Version 5.0) which occurs in any patient and is deemed related to the IMP by the treating investigator will result in that patient's trial treatment being discontinued. If patients develop Grade 3 neutropenia or more (according to the Common Terminology Criteria for Adverse Events (CTCAE) Version 5.0) they should be managed with granulocyte colony stimulating factor (GCSF) supplied via routine hospital pharmacy in accordance with local policy and prescribing practice. The study drug will be stopped and they will continue to be monitored until their full blood count recovers. They will not be recommenced on the study drug but will continue to be followed up within the trial.

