### **5.1.7 Pregnancy**

Artesunate is teratogenic in animal models and is contraindicated in the first trimester of pregnancy in humans. Pregnant women with malaria nevertheless are exposed to artesunate when no alternatives are available for treatment and studies published to date do not indicate an increased risk of teratogenicity. Pregnant women will not be recruited and participants will be required to use effective methods of medical contraception during the study. Women of child bearing age will be required to undergo a pregnancy test within 72 hours prior to commencing the study and must consent to adequate contraceptive methods from the time of consent and for up to 6 weeks following the end of IMP treatment.

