### **5.3 Withdrawal criteria**

Patients may discontinue study treatment or withdraw their consent to participate in the study at any time without prejudice. In consenting to the trial, participants are consenting to trial treatments, trial follow up and data collection. However, an individual participant may stop treatment early or be stopped early for any one of the following reasons :

- Unacceptable treatment toxicity or an adverse event
- Investigator decides that it is in the best interests of the patient to terminate his/her participation in the study
- Poor patient compliance and/or major protocol deviation
- Intercurrent illness that prevents further protocol treatment

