## 6.2 During treatment

### D7, D14, D22, D36, D43, D57

- Telephone consultation on D7, D36, D57
- Clinical Assessment on D14, D22, D43
- Speculum examination on D22,D43
- Concomitant medication on D14, D22, D43

- Patient self reported adverse events
- Safety blood test – FBC, U&E, LFT on D14, D22, D43,
- Study blood tests (plasma & PBMC) on D14
- Quality of Life Tool (European Quality of Life–5 Dimensions (EQ-5D)) D7, D14, D22, D43

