## 6.4 Summary table

Study Procedures	Screening prior to study entry	D1 Clinical review prior to start of medication	D7 Telephone consultation	D14 Clinical Review	D22 Clinical Review	D36 Telephone consultation	D43 Clinical Review	D57 Telephone consultation	D64 (+3 days) Clinical Review	D90 (+14 days) Clinical Review
Consent	X									
Medical History	X	X		X	X		X		X	X
Clinical Examination	X	X			X		X		X	X
Telephone consultation review			X			X		X		
Toxicity Assessment			X	X	X		X		X	X
Concomitant medication check		X	X	X	X		X		X	
Patient self-reported events (diary card)			X	X	X		X		X	X
Vital signs		X		X	X		X		X	X
Pregnancy Test		X								
Study medication check				X			X		X	
Safety Blood Test (FBC/renal/liver profile)		X		X	X		X		X	X
Study Blood test		X		X					X	X
Speculum examination					X		X		X	
Colposcopy examination + Cervical Biopsy		X								X
HPV Test		X							X	X
Vaginome + gut microbiome sample		X							X	X
Large Loop Excision Transformation Zone (LETTZ)										X
QOL Tools (EuroQol EQ-5D)		X	X	X	X		X		X	X

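### One pregnancy test, at D1, serves three cycles of a drug with a first-trimester contraindication, and Section 7.7 requires no action if a pregnancy occurs

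*Protocol*

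**What the plan says.** On risk, Sections 5.1.7 and 7.7 carry the same text. Both state "Artesunate is teratogenic in animal models and is contraindicated in the first trimester of pregnancy in humans", and both add, about pregnant women treated for malaria, that "studies published to date do not indicate an increased risk of teratogenicity".

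On testing, Section 7.7 says "Women of child bearing age will be required to undergo a pregnancy test within 72 hours prior to commencing the study". The inclusion criterion in Section 4.1 likewise asks only for a negative test before the first dose. In the Section 6.4 table, the row "Pregnancy Test" has one mark, in the D1 column. Section 6.2 lists "Safety blood test – FBC, U&E, LFT on D14, D22, D43" and no pregnancy test.

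On contraception, participants "must consent to adequate contraceptive methods from the time of consent and for up to 6 weeks following the end of IMP treatment".

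On stopping, Section 5.1.5 discontinues treatment for any related grade 3/4 reaction. For grade 3 or worse neutropenia it adds: "They will not be recommenced on the study drug but will continue to be followed up within the trial". Pregnancy is not named there or among the reasons in Section 5.3. The closest general reason in Section 5.3 is "Investigator decides that it is in the best interests of the patient to terminate his/her participation in the study".

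**The concern.** Section 7.7 sits in the pharmacovigilance chapter, where one expects to read what happens once a participant is found to be pregnant. It holds only entry and contraception rules already given in Section 5.1.7. The test schedule is fixed in the protocol itself, so this is not detail left for a later plan.

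If contraception fails, the schedule as written lets cycle 2 or cycle 3 begin in a pregnancy that nobody has looked for, during the trimester the protocol singles out. Whether the drug is then stopped, the sponsor told and the outcome learned rests on general clauses that do not mention pregnancy. The stake is participant safety and the completeness of the safety data, not the efficacy result.

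**Working it through.** The plan gives no figure of its own on this point, so the check is a reading of the schedule, day arithmetic and a bound on the expected number.

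**1. Dosing days.** Sections 3 and 5.1.1 give three 21-day cycles with dosing on the first 14 days.
- Cycle 1: D1 to D14.
- Cycle 2: starts 1 + 21 = D22, ends 22 + 13 = D35.
- Cycle 3: starts 22 + 21 = D43, ends 43 + 13 = D56.

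**2. Distance from the only scheduled test (D1).**
- To the start of cycle 2: 22 − 1 = 21 days.
- To the start of cycle 3: 43 − 1 = 42 days.
- To the last planned dose: 56 − 1 = 55 days.

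Sections 6.2 and 6.4 show that D22 and D43 are clinic visits at which safety blood is already taken.

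**3. What is mandatory for other events, and for pregnancy.**

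| Event | What the protocol requires |
|---|---|
| Related grade 3/4 reaction, or grade 3+ neutropenia | Drug stopped (5.1.5) |
| Overdose | SAE form to the sponsor (5.5) |
| Any death | Reported to the sponsor (7.4) |
| Birth defect | Serious by definition (7.3), so notified within 24 hours (7.4) |
| Related SUSAR | Reported however late it occurs (7.4) |
| Pregnancy itself | No stop, notification or outcome follow-up stated |

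The birth-defect and SUSAR rules act on an outcome. They work only if somebody learns of it. The last study visit is the Day 90 visit (5.8), and no section requires a pregnancy to be followed beyond it.

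**4. Expected number on treatment.** Inputs are the maximum enrolment of 28 (Protocol Summary) and 56 days from D1 to D56. Two further inputs are assumptions that the documents do not give: all 28 participants are of child-bearing potential, and contraception fails at 1 to 10% per year.
- Woman-years = 28 × 56 / 365.25 = 4.29.
- At 1% per year: 4.29 × 0.01 = 0.043.
- At 10% per year: 4.29 × 0.10 = 0.429.

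The expected number of conceptions between D1 and D56 is therefore about 0.04 to 0.43. A smaller share of child-bearing potential lowers it in proportion.

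**5. What rechecks at D22 and D43 would find.** Assume, again not from the documents, that a test turns positive 10 to 14 days after conception.
- The D43 test finds conceptions up to 43 − 14 = D29 or 43 − 10 = D33.
- Days of the 56 left uncovered: 56 − 33 = 23 to 56 − 29 = 27.
- Neither test can prevent exposure in cycle 1.

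The rechecks therefore reduce, but do not remove, the chance that a later cycle starts in an unrecognised pregnancy.

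**The case against.** The strongest reply has four parts.

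**Safeguards exist.** Pregnancy is excluded at entry and contraception is mandatory. Section 5.3 lets the investigator stop treatment. Section 7.3 allows other medically important situations to be handled as serious. Medical history is already taken at D22 and D43, so a direct question could be asked there. This stands as far as it goes: each route permits action, and none requires it for pregnancy. A reader might infer that reporting is left wholly to discretion. The documents do not support that, because a birth defect is a mandatory serious event and a related SUSAR has no time limit. Nor does the protocol state that pregnancy is a matter for judgement; it is silent, and only general clauses remain.

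**The follow-up window may not matter.** A reader might set the end of adverse event collection against the later end of the contraception window and infer a period of unmonitored risk. That inference is weak. The Day 90 visit may fall up to 14 days late (Section 6.3), which can carry it past the contraception window. Section 7.3 expects the drug to clear within 24 hours of stopping, so conceptions after the last dose would be largely unexposed. Only conceptions on treatment are counted here for that reason.

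**The risk is not established.** The protocol itself says published malaria studies show no increased risk. That stands, with the qualification in Section 5.1.8 that this regimen is much longer than usual malaria treatment and calls for close pharmacovigilance.

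**Other documents may cover it.** The safety-reporting SOP, the Malaysian guidelines, the product information, the reference safety document and the participant information were not available for this review, and they may contain pregnancy instructions. This stands for reporting and follow-up. It has less force for the test schedule, which the protocol fixes itself.

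**Conclusion.** The point holds as a cheap participant-safety improvement. The firm part is the schedule: one test at D1, then cycles starting 21 and 42 days later without a recheck, for a drug the protocol contraindicates in the first trimester. The absence of a mandatory stop, notification and outcome follow-up is a real gap in the text shown, but it depends more on documents that were not available.

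The size is small. The 0.04 to 0.43 conceptions expected on treatment is an upper bound in that it counts all 28 participants as being of child-bearing potential, and it rests on the assumed 1 to 10% annual contraceptive failure. It would be wrong to infer that the trial is likely to see an exposed pregnancy, or that the drug is known to cause harm in human pregnancy. The sample size, the primary endpoint and its analysis are not affected.

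**What to change.** 1. In Sections 6.2 and 6.4, for participants of child-bearing potential, add hCG to the safety bloods already taken at D22 and D43, or a urine test at those visits. Require the result before the first dose of the cycle. A urine test suits sites where the blood result is not back the same day.
2. Replace the duplicated text in Section 7.7 with a rule: study drug stops permanently on confirmed pregnancy; any pregnancy conceived between the first dose and the end of the contraception window is notified to the sponsor within 24 hours by the existing SAE route; and it is followed to outcome, even when that lies beyond the last study visit.
3. If an SOP or guideline already requires this, cite it in Section 7.7.

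The cost is amendment wording, one pregnancy form and at most 2 × 28 = 56 inexpensive tests, with no extra visit. If a pregnancy occurs, a few late contacts follow, and consent must cover them. Conceptions shortly before D43 or later will not be found by these tests, so the notification rule depends on participants reporting them and they should be asked to do so.
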